9.1.1 Statistical Hypothesis

No formal hypothesis testing is planned for this study. For efficacy endpoints, the study will provide the estimates and the associated 95% CI for precision.

9.1.2 Sample Size Rationale

Approximately 122 to 131 subjects are estimated to be recruited based on the number of study cohorts and the number of study subjects included in each cohort. Subjects not evaluable for DLT will be replaced, and this may result in the number of subjects enrolled being more than expected.

9.1.2.1 Dose Escalation Part

The maximum sample size in this phase will be determined jointly by the Sponsor and the investigator. The exact sample size of the mTPI-2 design in the dose escalation part cannot be pre-specified because of the dynamic nature of the Bayesian allocation procedure. Subjects not evaluable for DLT will be replaced, and this may result in the number of subjects enrolled being more than expected. It is estimated that approximately 27 to 36 subjects may be enrolled at this part.

9.1.2.2 Dose Expansion Part

In order to better describe the safety of the recommended dose of single-dose HMPL-306 in future studies, approximately 95 subjects (4 cohorts of approximately 20 subjects and 1 cohort [C-1] of approximately 15 subjects) will be treated with HMPL-306 during this part. For a given AE with a true rate of 10%, 5%, or 1%, the probability of observing at least 1 AE in 95 subjects is 100%, 99%, and 62%, respectively.

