4.1.2 Part 2 (Dose Expansion)

In the dose expansion part, 4 cohorts of subjects will receive HMPL-306 to further evaluate the safety, tolerability, PK, PD, and preliminary efficacy of HMPL-306 at MTD or RP2D in approximately 95 subjects with locally advanced or metastatic solid tumors with IDH mutations.

There will be approximately 20 subjects (15 subjects in Cohort C-1) in each of the following cohorts:

- **Cohort A:** Cholangiocarcinoma
- **Cohort B:** Skeletal chondrosarcoma
- **Cohort C:** Low-grade glioma
 - **Cohort C-1:** Perioperative glioma
- **Cohort D:** Any other solid tumor harboring an IDH mutation

Depending on preliminary efficacy, safety signals, or operational feasibility, the Sponsor in conjunction with the SRC may decide to reduce or increase enrollment in these cohorts.

Study Treatment

Subjects will receive HMPL-306 at MTD or RP2D for 28 days in each cycle until disease progression, death, intolerable toxicity, the investigator's judgement that the subject can no longer benefit from the study treatment, withdrawal of consent, loss to follow-up, death, or the end of the study, whichever occurs first.

Cohort C-1: Perioperative Glioma

This cohort will serve as an open-label, window of opportunity study to assess the concentration of 2-HG in surgically resected tumors following pre-surgical treatment with HMPL-306 when compared to untreated tumors. This cohort will enroll 15 subjects with recurrent low-grade glioma with IDH1 or IDH2 mutations who are candidates for surgical resection. Subjects will be randomized in a 2:1 fashion to receive either open-label HMPL-306 at the RP2D for 4 weeks prior to surgery or no treatment (control) for 4 weeks prior to surgery.

All subjects enrolled to this cohort will undergo pre- and post-treatment procedures as outlined in Table 2. All subjects will have the option of receiving HMPL-306 following surgery. Subjects with no residual disease following surgery will be allowed to receive HMPL-306 for up to 1 year or until disease progression, whichever occurs first. If residual disease is evident following surgery, those subjects may receive HMPL-306 until disease progression.

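### The Part 2 adverse-event detection figures count all 95 or so subjects as exposed, but about 5 Cohort C-1 controls receive HMPL-306 only if they opt in after surgery, so the 62% holds at the planned sizes only if all of them do

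*Protocol*

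**What the plan says.** Protocol Section 9.1.2.2 (Dose Expansion Part) counts about 95 subjects, made up of four cohorts of about 20 and all 15 in Cohort C-1, and states that they "will be treated with HMPL-306 during this part". At true AE rates of 10%, 5% and 1%, it then says that "the probability of observing at least 1 AE in 95 subjects is 100%, 99%, and 62%, respectively". The synopsis likewise describes HMPL-306 as given to about 95 Part 2 subjects, but it contains no detection probabilities.

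Section 4.1.2 (Part 2) describes Cohort C-1 differently. On size: "This cohort will enroll 15 subjects with recurrent low-grade glioma". On allocation: "Subjects will be randomized in a 2:1 fashion", either to HMPL-306 for 4 weeks before surgery or to "no treatment (control) for 4 weeks prior to surgery". After surgery, "All subjects will have the option of receiving HMPL-306 following surgery". The Cohort C-1 schedule of events (Table 2, footnote 1) also makes post-surgery treatment depend on the subject's choice.

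Section 9.1.3 restricts the safety analysis set to enrolled subjects who took at least one dose of study treatment.

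**The concern.** The sample-size sentence treats enrolled and exposed subjects as the same group. In Cohorts A, B, C and D that is reasonable, because every subject is assigned the drug. In Cohort C-1 it is not: one third of the subjects are randomised to a control arm with no pre-surgery drug. A control who declines treatment after surgery contributes nothing to the detection of drug-related events and is not in the safety set.

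Safety is the primary objective of Part 2, and Section 9.1.1 plans no hypothesis testing. The detection probabilities are therefore the only statistical support given for the Part 2 sample size, and they should rest on the number of subjects expected to be exposed. The figure most sensitive to that number is the one for rare events.

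**Working it through.** **Inputs**

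- Cohorts A, B, C and D: about 20 subjects each, so 4 × 20 = 80 (Sections 4.1.2 and 9.1.2.2).
- Cohort C-1: 15 subjects, randomised 2:1 (Section 4.1.2). Exact allocation gives 15 × 2/3 = 10 on HMPL-306 and 15 × 1/3 = 5 controls.
- True AE rates p: 10%, 5% and 1% (Section 9.1.2.2).

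**Formula**

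P(at least one event among n exposed subjects) = 1 − (1 − p)^n.

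**Step 1: reproduce the plan's figures at n = 80 + 15 = 95**

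- p = 10%: 1 − 0.90^95 = 1.0000, stated as 100%.
- p = 5%: 1 − 0.95^95 = 0.9923, stated as 99%.
- p = 1%: 1 − 0.99^95 = 0.6151, stated as 62%.

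All three agree, so the calculation is right for 95 exposed subjects.

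**Step 2: number planned to receive the drug**

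80 + 10 = 90, plus 0 to 5 controls who opt in after surgery.

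**Step 3: recompute**

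| Controls opting in | n exposed | p = 10% | p = 5% | p = 1% |
|---|---|---|---|---|
| 0 | 90 | 0.9999 | 0.9901 | 0.5953 |
| 1 | 91 | 0.9999 | 0.9906 | 0.5993 |
| 2 | 92 | 0.9999 | 0.9911 | 0.6033 |
| 3 | 93 | 0.9999 | 0.9915 | 0.6073 |
| 4 | 94 | 1.0000 | 0.9919 | 0.6112 |
| 5 | 95 | 1.0000 | 0.9923 | 0.6151 |

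**Step 4: size of the difference**

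For a 1% event, 61.5% − 59.5% = 2.0 percentage points, or 62% against 60% after rounding. Even four of five controls opting in gives 61.1%, which rounds to 61%. For 5% the difference is 99.2% − 99.0% = 0.2 points, and both round to 99%. For 10% both exceed 99.9%.

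**The case against.** Several counter-arguments deserve a hearing.

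*It is not a calculation error.* This stands. A reader might infer from the mismatch that the 62% was computed wrongly. It was not: Section 9.1.2.2 states the probability for 95 subjects, and the formula returns it. What is at fault is the assumption that 95 subjects are exposed.

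*The numbers are approximate and adjustable.* This stands in part. The synopsis plans about 20 evaluable subjects per cohort. Section 6.2.1.3 allows replacement of Part 2 subjects who are not eligible for response assessment, and a replaced subject who took a dose stays in the safety set. Five such replacements in Cohorts A to D would bring exposure back to 95 with no control opting in. Section 4.1.2 also lets the sponsor, with the Safety Review Committee, enlarge or shrink the cohorts. It is therefore tempting, but unsupported, to read 90 and 95 as guaranteed lower and upper limits; they are what the planned cohort sizes imply. These provisions are discretionary, though, and Section 9.1.2.2 relies on none of them. The word approximately covers variation in enrolment. It does not cover a randomised untreated arm that is known in advance, and the sentence expressly counts all 15 Cohort C-1 subjects as treated.

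*Controls may take the drug later.* True, and those who do will count in the safety set, although their exposure begins only after surgery. Nothing in the documents obliges them to do so.

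*Nothing depends on the figure.* Largely true. No test, stopping rule or decision threshold uses the 62%, and nothing suggests that a different size would have been chosen at 60%.

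**Conclusion.** The point holds as a small inconsistency in the exposed denominator. At the planned cohort sizes about 90 exposures are planned, not 95, and the stated 62% for a 1% event is reached only if all of about 5 Cohort C-1 controls opt for HMPL-306 after surgery. With none opting in, the figure is 59.5%. The figures for 5% and 10% events stand as printed.

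This rests on three assumptions: exact 2:1 allocation of 15 subjects, all 80 subjects in the other four cohorts being dosed, and no replacement or change in cohort size.

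Two further readings go beyond the documents. First, a reader might infer that the Part 2 sample size is inadequate; a 2-point change in one descriptive probability does not show that. Second, a reader might infer that reported results are affected. SAP Sections 1 and 7 state that no patients entered any expansion cohort, so the point concerns the protocol's stated rationale only.

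**What to change.** In Section 9.1.2.2, separate enrolment from exposure. State that approximately 95 subjects will be enrolled in Part 2, that approximately 90 of them are planned to receive HMPL-306, and that up to about 5 Cohort C-1 controls may be added if they opt in after surgery. Give the detection probabilities for n = 90: above 99.9%, 99% and 60% for true rates of 10%, 5% and 1%. Keep the word approximately, so that 90 and 95 are not presented as firm limits.

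In the synopsis, align the description of who receives the drug in Part 2. It has no probabilities to correct.

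The cost is one reworded sentence, one changed percentage and a matching edit in the synopsis, with a slightly less favourable figure for rare events. Sample size, randomisation and treatment rules stay as they are. The SAP cites Amendment 3, whereas the protocol text reviewed here is Amendment 2. The sponsor should therefore check whether the sentence is still present, and correct it before the rationale is reused.

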9.1.3 Analysis Sets

The following analysis sets are defined for the study:

- Safety analysis set: All enrolled subjects who received at least 1 dose of study treatment will be included in the safety analysis population. Safety evaluation will be performed based on the first dose of study treatment received by a subject. This is the primary population for the safety and efficacy analysis endpoint PFS.

- DLT evaluable analysis set: All subjects enrolled in the dose escalation phase of the study who are evaluable for DLT assessment. A subject is DLT evaluable if he/she meets the following criteria:
 - has received at least 75% of the assigned dose of study medication during the DLT assessment window
- OR
- has not completed the DLT assessment period due to a DLT
- Response evaluable analysis set: All subjects who received study treatment and have a baseline tumor assessment and at least 1 postbaseline assessment will be considered evaluable for antitumor efficacy endpoints such as objective response rate (ORR), disease control rate (DCR), time to response (TTR), and duration of response (DoR)
- PK analysis set: All subjects with at least 1 quantifiable plasma concentration of HMPL-306 will be included in the PK analysis population
- PD analysis set: All subjects with at least 1 quantifiable level of 2-HG in the plasma will be included in the PD analysis population

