Visit			D1	D8	D15	D22	D28 (Day prior to surgery)		D1	D15	D1	D15	D1	Within 7 Days After the Last Dose	30 Days After the EOT Visit	Every 12 Weeks From EOT Visit
Visit Window (days)	--	-28 to -1	--	±1	±1	±1	--		±3	±3	±3	±3	±3	±3	±7	±14
Activities																
Pregnancy test ¹⁵		X	X				X		X		X		X	X	X	
Urinalysis ^{15,16}		X ¹¹					X		X		X		X			
Virological screening ¹⁷		X														
HbA1C		X ¹¹			X		X		X		X		X			
PK and PD assessments ¹⁸			Refer to Appendix 2													
12-lead ECG ^{7, 19}		X	Refer to Appendix 2													
ECHO/MUGA scan		X							X		X		C3D1 then Day 1 of every odd cycle (ie, C5D1, C7D1, etc.) (± 1 week)			
Tumor evaluation/imaging ²⁰		X						X within 2 weeks post op	Every 8 weeks from C1D1 during the first 24 (±1 week) weeks and every 12 (±2 weeks) weeks thereafter							X
Blood for gene mutation analysis		X							Refer to Appendix 2							
Study drug administration			HMPL-306 will be dosed at the RP2D						HMPL-306 will be dosed at the RP2D							
AEs ²¹	X	X	X	X	X	X	X	X	X	X	X	X	X	X	X	

AE = adverse event; ALP = alkaline phosphatase; ALT = alanine aminotransferase; aPTT = activated partial thromboplastin time; AST = aspartate aminotransferase; C = cycle; CMV = cytomegalovirus; D = day; DNA = deoxyribonucleic acid; ECG = electrocardiogram; ECHO = echocardiogram; ECOG = Eastern Cooperative Oncology Group; eCRF = electronic case report form; EOT = end of treatment; HBcAb = hepatitis B core antibody; HBsAb = hepatitis B e-antibody; HBsAg = hepatitis B e-antigen; HBsAb = hepatitis B surface antibody; HBsAg = hepatitis B s-antigen; HBV = hepatitis B virus; HCV = hepatitis C virus; HIV = human immunodeficiency virus; IDH = isocitrate dehydrogenase; INR = international normalized ratio; LDH = lactate dehydrogenase; MUGA = multigated acquisition; NGS = next-generation sequencing; PCR = polymerase chain reaction; PD = pharmacodynamic(s); PI = principal investigator; PK = pharmacokinetic(s); PT = prothrombin time; RNA = ribonucleic acid; RP2D = recommended phase 2 dose; SAE = serious adverse event.

1. If the subject chooses to continue treatment with HMPL-306, C1 will begin 4 to 8 weeks after surgery based on the clinical judgment of the PI.
2. Pre-screening informed consent is signed to obtain IDH mutational status report. Subjects who have already tested positive for IDH mutation may enter the Screening period directly.

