6.1.13 Tumor Assessment

Tumor time point response assessment will be performed by the investigators according to RECIST Version 1.1 ([Appendix 8](#)) or RANO criteria for glioma subjects ([Appendix 9](#)). The tumor assessments will be performed during screening, every 8 weeks (± 1 week) beginning on C1D1 for the first 24 weeks, and every 12 weeks (± 2 weeks) thereafter as specified in [Table 1](#) and [Table 2](#), through EOT or end of Efficacy Follow-up (if applicable).

All measurable and evaluable lesions should be assessed and documented using image-based evaluation. All subjects are to be evaluated utilizing contrast-enhanced computed tomography (CT) scan or positron emission tomography (PET) scan or Gd MRI for glioma subjects to identify and follow selected lesions throughout the study. In addition, other radiographic or scintigraphic procedures (such as radionuclide bone scans), as deemed appropriate by the investigator, will be performed to assess sites of neoplastic involvement.

Tumor assessments completed as standard of care prior to signing of the informed consent but, within 28 days of first dose of study treatment, may be used as baseline scans. Assessments throughout the study should be made using the same modality as used at Screening.

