9.2.7 Efficacy Analysis

The investigator shall evaluate efficacy according to the corresponding criteria for all subjects according to RECIST Version 1.1 (RANO criteria for glioma subjects).

Efficacy evaluation indicators include ORR, DCR, DoR, TTR, PFS, and OS.

- ORR: Defined as the proportion of subjects achieving a best overall response of confirmed complete response (CR) or partial response (PR)
- DCR: Defined as the proportion of subjects achieving a best overall response of confirmed CR, PR, or stable disease (SD)
- DoR: Defined as the time from the first occurrence of PR or CR, whichever comes first until disease progression or death
- TTR: Defined as the time from the start of study treatment to the first occurrence of objective response (PR or CR, whichever comes first)
- PFS: Defined as the time (months) from the start of study treatment until the first radiographic documentation of objective progression as assessed by the investigator using RECIST Version 1.1 or death from any cause
- OS: Defined as the time from the start of the study drug until death from any cause

The estimate of ORR and DCR and the corresponding 95% CI will be presented by tumor type. For time-to-event endpoints such as PFS, TTR, DoR, and OS, the medians and rates at various time points along with 95% CI will be estimated by Kaplan-Meier methodology.

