APPENDIX 9 RESPONSE ASSESSMENT IN NEURO-ONCOLOGY CRITERIA FOR GLIOMAS

Patients should be assessed with the same imaging method throughout the trial, with pre-specified imaging parameters.

General minimum imaging protocol of low-grade glioma:

Basic Magnetic Resonance Imaging Protocol (All Centers)

- Axial fluid-attenuated inversion recovery (FLAIR) (canthomeatal alignment): 3- to 5-mm sections, 1-mm interslice gaps, slice registration preserved as much as possible between sequential studies
- Axial T2: 5-mm sections, 1-mm interslice gap
- Coronal T1: 5-mm sections, 1-mm interslice gap
- Post-gadolinium chelate (contrast agent as per local clinical practice): coronal T1 and axial T1

(Alternatively, pre-gadolinium and post-gadolinium volumetric T1 may replace axial and coronal T1-weighted sequences)

Response	Criteria
Complete response	Complete response requires all the following criteria compared with the baseline scan: 
 • complete disappearance of the lesion on T2 or FLAIR imaging (if enhancement had been present, it must have resolved completely) • no new lesions, no new T2 or FLAIR abnormalities apart from those consistent with radiation effects, and no new or increased enhancement • patients must be off corticosteroids or only on physiological replacement doses • patients should be stable or improved clinically.
Partial response	Partial response requires all of the following criteria compared with the baseline scan: 
 • greater than or equal to 50% decrease in the product of perpendicular diameters of the lesion on T2 or FLAIR imaging sustained for at least 4 weeks compared with baseline • no new lesions, no new T2 or FLAIR abnormalities apart from those consistent with radiation effects, and no new or increased enhancement • patients should be on a corticosteroid dose that should not be greater than the dose at time of baseline scan, and should be stable or improved clinically.

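### Cohort C-1 has no rule for its planned resection, so surgery can be scored as HMPL-306 response, and the start point for PFS and TTR is contradictory

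*Protocol*

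**What the plan says.** **Endpoints.** Table 4 (Protocol section 3) sets ORR, DCR, DoR, TTR and PFS for Part 1 and Part 2, with no exception for C-1. Other rows of that table are restricted by cohort: OS to A, B and D, and two rows to C-1 alone.

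**Cohort C-1 (4.1.2).** The cohort has 15 subjects with recurrent glioma who are fit for an operation. On allocation the section states: "Subjects will be randomized in a 2:1 fashion to receive either open-label HMPL-306 at the RP2D for 4 weeks prior to surgery or no treatment". Untreated subjects serve as controls. Post-surgical HMPL-306 is optional in both arms. The section expects that some subjects will have no residual tumor after the operation. Table 2, footnote 1, adds that for those who continue, "C1 will begin 4 to 8 weeks after surgery based on the clinical judgment of the PI".

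**Scans.** Table 2 schedules one scan before surgery (Screening), one within 2 weeks after it, and then scans counted from C1D1. Section 6.1.13 says that standard-of-care scans "within 28 days of first dose of study treatment, may be used as baseline scans".

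**Response.** The evaluable set (9.1.3) is "All subjects who received study treatment and have a baseline tumor assessment and at least 1 postbaseline assessment will be considered evaluable". In Appendix 9, "Partial response requires all of the following criteria compared with the baseline scan". Appendix 9 exempts radiation effects from the new-abnormality criterion but does not mention resection.

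**Time origin.** Section 9.2.7 runs PFS and TTR from the start of study treatment. Section 6.1.3 and Table 2, footnote 8, identify the start of treatment with C1D1, which in C-1 comes after surgery.

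**Presentation.** Section 9.2.7: "The estimate of ORR and DCR and the corresponding 95% CI will be presented by tumor type". Section 9.2 summarizes by dose/disease cohort.

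**The concern.** The objective is the antitumor activity of HMPL-306. In C-1 a planned operation removes tumor between the Screening scan and every later scan. If the Screening scan is the baseline, the endpoint cannot separate what the surgeon removed from what the drug did. ORR, DCR, TTR and DoR would then describe surgery plus drug under the drug's name.

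PFS and TTR have a second problem. The protocol gives two incompatible answers to when treatment starts for a subject dosed before surgery, so two programmers could derive different values from the same record. At stake is the reading of a small descriptive cohort, and of glioma as a tumor type if C and C-1 are shown together.

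**Working it through.** The plan states no expected response or PFS figure for C-1. Its only probability statement for Part 2 (9.1.2.2, at least one AE in 95 subjects) reproduces: 1 − (1 − p)^95 gives 99.996%, 99.2% and 61.5% for p = 10%, 5% and 1%, against the stated 100%, 99% and 62%. It does not bear on this point.

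**1. Arms.** 15 subjects at 2:1 gives 10 on HMPL-306 and 5 controls.

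**2. Order of events (Table 2).** D28 is the day before surgery, so surgery is D29. C1D1 is 28 to 56 days later: D57 to D85.
- HMPL-306 arm: Screening scan, first dose D1, resection D29, post-operative scan, C1D1 if the subject continues.
- Controls: Screening scan, resection, post-operative scan, first dose at C1D1 if the subject opts in.

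**3. Response.** In the HMPL-306 arm the only scan before first dose is the Screening scan, so all later scans are compared with the unresected tumor. For controls who opt in, a Screening baseline has the same effect; a post-operative baseline does not. The protocol does not say which applies.

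Suppose the drug has no effect and k of the 10 treated subjects meet RANO CR or PR through surgery. The arm ORR is k/10 (Clopper-Pearson 95% CI):

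| k | Arm ORR | 95% CI |
|---|---|---|
| 0 | 0% | 0–31% |
| 3 | 30% | 7–65% |
| 5 | 50% | 19–81% |
| 8 | 80% | 44–98% |
| 10 | 100% | 69–100% |

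The documents give no extent of resection, so k is unknown.

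**4. Pooled glioma (only if C and C-1 are combined).** Assume 3 responders of 20 in Cohort C (15%, close to the 13.6% cited in Appendix 11) and add the 10 treated C-1 subjects: (3 + k)/30 is 10%, 27% and 43% at k = 0, 5 and 10.

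**5. Time origin.** Two readings:
- Sections 9.2.7 and 9.1.3 with Table 2 dosing: D1 in the HMPL-306 arm, C1D1 in controls. The offset is 57 − 1 = 56 to 85 − 1 = 84 days, or 1.84 to 2.76 months (÷ 30.4375). Progression at the first scan 8 weeks after C1D1 is then PFS of (56 + 1)/30.4375 = 1.87 months in a control, but (56 + 56 + 1)/30.4375 = 3.71 to (84 + 56 + 1)/30.4375 = 4.63 months in a treated subject.
- Section 6.1.3 and Table 2, footnote 8: C1D1 in both arms, offset zero. Treated subjects who stop after surgery then have no start date.

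**6. Can the existing scans serve as baseline?** At a control's first dose the Screening scan (D−28 to D−1) is 57 to 112 days old. The post-operative scan is 14 to 28 days old if C1 starts at week 4 and 42 to 56 days old if it starts at week 8. Neither reliably meets the 28 days in 6.1.13.

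**The case against.** The case against has real force on several points.

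- **A reader might infer that the arms definitely have different PFS origins.** The text does not settle that. Section 6.1.3 and Table 2, footnote 8, point to C1D1 for everyone. The 56 to 84 days are one reading of passages that conflict.
- **A reader might infer that removing half the lesion is by itself a partial response.** Appendix 9 also requires the decrease to last at least 4 weeks, no new or increased enhancement, no new lesions, a corticosteroid limit and clinical stability, and 9.2.7 requires confirmation. One post-operative scan is not enough. These conditions narrow the problem, but a durable resection in a stable patient can satisfy them all.
- **A reader might take 10/15 = 67% as the C-1 ORR produced by surgery.** That is an extreme case. It assumes every treated subject is scored through surgery, all five controls opt in, and none of them is scored. If no control opts in, the same scenario is 10/10.
- **A reader might infer that the plan pools C with C-1.** Presentation by tumor type permits this. Section 9.2 summarizes by disease cohort and 9.1.2.2 counts C-1 as its own cohort, so separate display is equally open.
- **The efficacy baseline is not firmly defined.** The wording in 6.1.13 permits use of pre-consent scans, and the SAP's last-value-before-dose rule (4.1.2) is in a plan for Part 1 only. This weakens a claim of asymmetry between arms. But if Screening is the baseline for everyone, the problem extends to controls.
- **Consequences are limited.** There is no hypothesis test (9.1.1) and no planned between-arm efficacy comparison. Protocol 9.1 left analysis detail to the SAP, and the SAP covers Part 1 only. The SAP also cites Amendment 3, while the protocol reviewed is Amendment 2.

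What remains is that no passage keeps the resection out of the response endpoints, and the passages on treatment start disagree.

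**Conclusion.** The concern holds as an omission plus a contradiction. As written, Part 2 applies response and PFS endpoints to a cohort with a planned resection, without saying which scan is baseline, whether surgical change counts, or when the clock starts. Following the plan can therefore score surgery as HMPL-306 response.

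The response bias cannot be sized from the documents; with no drug effect the treated-arm ORR could lie anywhere from 0% to 100%. The time-origin discrepancy is 0 or 56 to 84 days, depending on which passages govern.

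The damage is confined to descriptive C-1 estimates, and to glioma estimates only if C and C-1 are pooled. The C-1 primary comparison of 2-HG is unaffected. A reader might infer that trial results are compromised. They are not: SAP sections 1 and 7 state that no subject entered C-1, so no reported result changes. The point matters for the protocol as a design, and for any reuse of it.

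**What to change.** In Protocol 9.1.3 and 9.2.7, cross-referenced from 6.1.13 and Appendix 9:

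1. State that change in tumor size from before to after surgery in C-1 is not counted as response.
2. Report C-1 separately from Cohort C in all estimates by tumor type.
3. Choose one of two options for ORR, DCR, DoR and TTR. Either leave C-1 out, or present them descriptively only in subjects who take post-surgical HMPL-306, with the already scheduled post-operative scan as baseline. In the second case, say that the 28-day limit in 6.1.13 does not apply to that scan, and exclude subjects without measurable residual disease from the response endpoints.
4. Define one time origin for PFS and TTR in C-1, for example post-surgical C1D1. List earlier progressions, and subjects who decline post-surgical drug, separately.
5. Reconcile 6.1.3 and Table 2, footnote 8, with 9.2.7 and the pre-surgical dosing in Table 2.

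The cost is wording; no scan is added. The downsides are fewer response-evaluable subjects, a less favourable ORR, and a C-1 PFS that is conditional on reaching post-surgical treatment and should be labelled so.
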